## Participant flow through the trial

### KEY

V#	Visits number	GUT	Stool collection Continuous glucose monitoring
C&S	Consent and screening	CGM	
Blood	Blood sampling	HRV	Heart rate variability
SPO2	Oxygen saturation	Accel	Physical activity and sleep
Hypoxic	Hypoxic screening	Diet	Diet diaries
DEXA	Body composition	Urine	Urine samples
OGTT	Oral glucose tolerance test		

## 10.1 Recruitment

Our typical recruitment rates via GP practices is approximately one in ten people with T2DM. GP recruitment will be executed via mail outs and text messages (e.g. We are looking for people with type 2 diabetes to sleep at home in slightly reduced oxygen for 10 nights which may help manage their diabetes and help them lose weight - click the link to find out more). Recruitment via the local DESMOND course (T2DM education clinic) is approximately one in five people with T2DM. We will need to approach between 90 and 113 people with T2DM to ensure we recruit enough (n = 23) people to account for drop outs.

## 10.2 Screening and Enrolment

For word of mouth recruits, the research team will provide interested parties with an invitation letter and the PIS. Our local GP collaborators will send our PIS and a letter which will include a free post return slip for potential participants who are interested. A member of the UoP research team will attend the DESMOND meeting 3 times a month to advertise, discuss and disperse information about the study.

For actual participant screening following consent, please see part 10 (one page above).

## 10.3 Randomisation

Eligible participants will be randomly allocated (using randomizer.org) to start in either the hypoxia or sham condition (see details below).

## 10.4 Study Assessments

### **OGTT**

Fasted blood samples will then be taken for the measurement of plasma glucose and insulin concentrations ([glucose] and [insulin], respectively), and these data will be used to calculate  $\beta$ -cell function via the HOMA-%B model. Following this, participants will consume 75 g of glucose, and blood samples will be taken at 0 and 120 minutes post-glucose ingestion for the assessment of plasma [glucose] and [insulin]. Utilising the data from the OGTT protocol, insulin sensitivity of those not on insulin will be estimated using Stumvoll's insulin sensitivity index [31].

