### 7.2 Primary and Secondary Endpoints/Outcome Measures

#### *Primary outcome measure*

Post-intervention (sham vs hypoxia) area under curve for venous blood [glucose] during a 2 hour OGTT.

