#### *Secondary outcome measures*

Fasting venous blood [glucose] peak venous blood [glucose] during OGTT, Homeostatic Model Assessment for Insulin Resistance (HOMA-IR), daily glucose excursions (continuous glucose monitoring), and untargeted metabolomics, body mass / composition change, hormonal markers of appetite (e.g. leptin and ghrelin), food intake, gut microbiome, markers of inflammatory status (e.g. interleukin-6; nitrite), redox balance (TNF $\alpha$ ; SOD), HIF-1 $\alpha$ , extracellular HSP70, physical activity and sleep quality.

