## 9. SAMPLING

The study of 20 subjects provides adequate power (including a 15% drop-out rate typically seen in our clinical trials): 13 subjects are required to detect a 1 standard deviation change [30] in venous blood [glucose] during a 3 hour oral glucose tolerance test (OGTT (alpha = 0.05; power = 80%)). Seasonal changes will be recorded and corrected for as a covariate.

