Visits 2-5 are identical in nature. Visits 2 and 4 are baseline visits before each arm of the crossover (i.e. the intervention). Visits 3 and 5 are following the 10 day hypoxic or sham exposures to assess the outcomes. An OGTT, body composition and venous blood samples and a stool collection will occur on each visit. After visit 3 there will be a 4 week washout out period. Visit 4 is necessary to ensure participants are back to baseline. During this visit, if anyone has had a respiratory tract infection or infectious disease in between visits, the hypoxic screening and lung function tests will be repeated. During visit 3, a new CGM sensor will be secured and accelerometer worn and a home visit for set-up will be re-booked. At the end of visit 5, another CGM and accelerometer will be affixed to the participants to check how long the effects of the intervention take to decay.

Urine collection is critical for our metabolomics analysis. In order to look for trends across time and between conditions we will need to collect urine before, during and after the intervention. Participants will be asked to collect a small urine sample for 2 days before the intervention starts, for each day of the intervention and for 2 days following the intervention. Participants will be provided with instructions on how to collect a mid-flow urine sample and how to safely store the samples until they are collected.

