### **Continuous glucose monitoring (CGM)**

The sensors (Abbott Diabetes Care Inc., Alameda, CA, USA) will be fixed to the anterior portion of the upper arm with a small adhesive patch. These sensors will be worn for 14 days to determine free-living glycaemic control.

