### 14.2 Analysis of Endpoints

All data will be tested for normality using the Shapiro-Wilk test. For normally distributed data, paired samples t-tests will be used to assess differences pre and post hypoxic exposures for; blood [glucose] (AUC and peak), insulin sensitivity, eHSP70, IL-6, leptin, ghrelin, TNFa, SOD, HIF-1 $\alpha$  HR, PA and sleep efficiency. For non-parametric data Wilcoxon-Signed rank test will be used for pairwise comparisons. Repeated measures one-way analysis of variance (ANOVA) will be used to identify differences between conditions for SpO2 and [glucose] across time from the CGMs. Mauchly's test of sphericity will be used to determine if any data violated the assumption of spherical data. If violated, sphericity will be accounted for using the Greenhouse-Geisser correction. Where significant differences are observed ( $P < 0.05$ ), post-hoc tests will be performed using LSD pairwise comparisons. Effect sizes will be reported as partial eta squared ( $\eta^2_p$ ) (small = 0.01; medium = 0.06; large = 0.14) [33].

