## **20. DISSEMINATION AND OUTCOME**

Results (estimates of effect sizes and confidence intervals) from this pilot study will be utilised to define our primary outcome and to power a larger, definitive multi-centre randomised control trial with our co-applicants and collaborators around Europe. Once our final report has been submitted to the funder, we will apply for NIHR funding via a researcher-led Research for Patient Benefit (RfPB) or an Efficacy and Mechanism Evaluation (EME) bid (depending on the effect size and sample size). The results will be disseminated through publication in peer-reviewed scientific and clinical journals and via presentations, local, national and international meetings. A summary of the results will be sent to all the participants. Finally, an open day and presentation will be carried out where the participants will be informed of the study findings and have the opportunity to ask any pertinent questions and/or provide feedback.

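### OGTT blood draws at 0 and 120 minutes only do not support the primary glucose AUC or the peak-glucose endpoint, and no AUC formula is given

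*Combined protocol and SAP*

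**What the plan says.** Section 7.2 defines the primary outcome as "Post-intervention (sham vs hypoxia) area under curve for venous blood [glucose] during a 2 hour OGTT"; the synopsis repeats it, and section 6.1 sets the same objective. Section 7.2 also lists "peak venous blood [glucose] during OGTT" as a secondary outcome, as do the synopsis, section 6.2 and the Biochemistry part of section 10.4. Section 14.2 names "blood [glucose] (AUC and peak), insulin sensitivity" among the variables for the paired t-test, with the Wilcoxon signed-rank test as the alternative.

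The draws themselves are described once, under OGTT in section 10.4: a fasted sample, 75 g of glucose, then "blood samples will be taken at 0 and 120 minutes post-glucose ingestion for the assessment of plasma [glucose] and [insulin". The description of visits 2 to 5 in section 10 adds no times; it says only that "An OGTT, body composition and venous blood samples and a stool collection will occur on each visit".

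The text nowhere states whether the AUC is total or incremental, or which integration rule applies. Section 14.4 says no analysis plan is needed beyond section 14, so there is no separate SAP to settle it.

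**The concern.** An AUC is meant to summarise the glucose curve between the fasting and 2-hour values, and a peak is meant to be found somewhere along that curve. Two draws at the ends of the interval carry no information about what happens between them. Staff who followed section 10.4 to the letter would report a rescaled sum or difference of fasting and 2-hour glucose under the name AUC, and the larger of the same two numbers under the name peak. Fasting glucose is already a secondary outcome in its own right, so three named endpoints would be built from one pair of measurements.

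Continuous glucose monitoring does not fill the gap. The endpoint is venous, and section 10.4 assigns the sensors a different job: they are "worn for 14 days to determine free-living glycaemic control".

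The open formula is a second problem. Total and incremental AUC can give different answers from the same data, and an analyst who chooses after seeing the results has an uncontrolled choice on the primary endpoint.

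Section 20 raises the stakes, because estimates from this pilot "will be utilised to define our primary outcome and to power a larger, definitive multi-centre randomised control trial". Samples that were not drawn cannot be recovered afterwards.

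**Working it through.** The plan gives no AUC value, so there is no figure of its own to reproduce. The algebra in steps 1 to 3 needs no assumed data. Steps 4 and 5 are illustrations on assumed values.

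**Step 1. What two draws give.** Write G0 and G120 for glucose at 0 and 120 minutes (section 10.4).

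- Total trapezoid: 120 × (G0 + G120)/2 = 60 × (G0 + G120).
- Incremental: 60 × (G0 + G120) − 120 × G0 = 60 × (G120 − G0).
- Peak: max(G0, G120).

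**Step 2. Compared with a five-point schedule.** Take draws at 0, 30, 60, 90 and 120 minutes (an assumed comparator; the plan gives none).

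- Trapezoid weights are 15, 30, 30, 30 and 15 minutes, so the middle three samples carry (30 + 30 + 30)/120 = 75% of the weight.
- With two draws the weights are 60, 0, 0, 0 and 60, and the middle carries 0%.
- Five-point minus two-point total AUC = 30 × (G30 + G60 + G90) − 45 × (G0 + G120).

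**Step 3. Total or incremental.** Suppose glucose falls by 1.0 mmol/L at every time. Total AUC changes by −1.0 × 120 = −120 mmol/L·min. Incremental AUC changes by −120 + 120 × 1.0 = 0.

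**Step 4. Assumed curves (mmol/L at 0/30/60/90/120 min).**

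| Curve | Five-point AUC | Two-point AUC | True peak | Recorded peak |
|---|---|---|---|---|
| A: 9, 13, 16, 16.5, 15 | 1725 | 1440 | 16.5 | 15 |
| B: 9, 12, 14, 14.5, 15 | 1575 | 1440 | 15 | 15 |
| C: 9, 13, 16, 16.5, 13 | 1695 | 1320 | 16.5 | 13 |

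A and B differ by 150 mmol/L·min on five points and by 0 on two. A and C differ only at 120 minutes: the five-point AUC falls by 30 and the two-point AUC by 120. Two draws therefore hide a mid-curve difference and magnify a difference at the end. Where the peak falls between draws (A and C), it is understated by 1.5 and 3.5 mmol/L.

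**Step 5. Illustrative power.** Two-sided 5% paired t-test, noncentral t, n = 19 (23 × 0.85 = 19.55, rounded down; df 18). Assumed: SD of the paired difference 1.5 mmol/L at each time, and serial correlation between 30-minute steps from 0.3 to 0.85 (first-order autoregressive).

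| Assumed effect (mmol/L) | AUC | Five points | Two points |
|---|---|---|---|
| 1.0 at every time | total | 86–99.6% | 88–97% |
| 0.2, 0.8, 1.2, 1.2, 0.8 | total | 81–99% | 35–49% |
| 1.2 at 30–90 min only | total | 78–98.5% | 5% |
| 1.0 at every time | incremental | 5% | 5% |
| 0.2, 0.8, 1.2, 1.2, 0.8 | incremental | 56–93% | 22–39% |

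With SD 2.5 instead, total AUC gives 45–79% versus 47–64% for the uniform effect and 40–72% versus 16–21% for the varying effect; incremental AUC gives 24–54% versus 11–17% for the varying effect. The uniform effect is therefore not wholly protected: at SD 2.5 and correlation 0.3, power is 78.8% with five points and 64.2% with two.

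**The case against.** The strongest reply is that section 10.4 may be loose drafting for sampling across the whole 0 to 120 minutes. Every mention of AUC and peak presupposes a curve. The study flow figure is not shown, and the schedule of procedures, flow chart and data collection forms (Appendices 1, 2 and 6) are not in the text available. Those are natural places for draw times. This stands as a limit on the claim: the text shows that section 10.4 does not match the endpoints, not that only two tubes were drawn. It does not remove the need for correction. If an appendix lists intermediate draws, section 10.4 contradicts it, and the AUC definition is still absent from section 14.

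Three further points are fair:

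- A two-point AUC can be computed. The fault is that it is mislabelled and blind to the middle of the test.
- The SDs, correlations and effect shapes behind the power figures are all assumed, so those figures do not bound the loss in this trial. The algebra carries the argument.
- Section 20 leaves the definitive trial's primary outcome open, so a two-point AUC need not be carried into it. Effect sizes from one could still misinform that choice.

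The OGTT length in section 9, which refers to "venous blood [glucose] during a 3 hour oral glucose tolerance test", is a separate mismatch. That section also still gives 20 subjects where the synopsis and section 8.2 give 23, so it may simply not have been updated. It adds no weight here.

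**Conclusion.** The concern holds for the plan as written. The one stated sampling schedule reduces the primary endpoint to a function of fasting and 2-hour glucose, makes peak unobservable unless it falls on a draw, and leaves two candidate AUC formulas that can disagree completely. These conclusions follow from sections 7.2, 10.4 and 14.2 by arithmetic alone. How much power is lost cannot be fixed from the documents: under the assumptions shown, it runs from little or none for an effect that is equal at all times to complete for one confined to 30 to 90 minutes. Because the primary endpoint is affected and undrawn samples are lost for good, this must be fixed. The one reservation is that draw times may appear in an appendix or figure that was not available.

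**What to change.** **Preferred.** In section 10.4, list every venous sampling time for the OGTT at visits 2 to 5, including times between 0 and 120 minutes (for example 30, 60 and 90). In section 14.2, define the AUC as total or incremental, by the trapezoidal rule over those times, and say how a missed draw is handled.

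**If only two draws are kept.** Rename the primary endpoint as what is measured, for example 2-hour glucose, and delete peak glucose from the synopsis and sections 6.2, 7.2, 10.4 and 14.2.

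**If the times already stand in an appendix.** Bring section 10.4 into line with it and add the AUC definition.

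Separately, reconcile the 3-hour test in section 9 with the 2-hour test in the synopsis and section 7.2.

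**Cost.** Three extra draws at four visits for 23 participants is at most 3 × 4 × 23 = 276 samples. That means 276 glucose assays, or 552 assays if insulin is measured at each draw as section 10.4 implies. Participants already wait for the 120-minute sample, so no visit is added. The extra blood volume, the repeated venepuncture or cannulation, and the fixed $120,000 of funding in section 17 should be weighed. Renaming or realigning costs only wording.

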### **Dual-energy X-ray absorptiometry (DEXA) scanner**

The scan will be carried out using a DEXA scanner (Holologic, Vertec, UK) operated by a trained and qualified researcher ([name]). A whole body scan will be conducted on each participant and a post-collection segmental analysis will be conducted afterwards. Variables that will be calculated from the scan data are fat density, muscle density and bone density; the scan will produce a density value measured in  $\text{g}\cdot\text{cm}^{-3}$ . This will give us a baseline analysis of body composition and will allow us to identify if the expected weight loss of the intervention is fat or fat free mass.

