#### 4. BACKGROUND AND RATIONALE

Type 2 diabetes mellitus (T2DM) is a metabolic condition characterized by progressive insulin resistance and chronic hyperglycemia (high blood glucose concentrations) (10). Hyperglycaemia increases the risk of both micro- and macrovascular damage, whilst interventions that reduce blood glucose mitigate this risk (32). Weight loss, achieved through exercise and dietary modification, is effective at reducing hyperglycaemia (22). However, despite the clear benefits of exercise and weight loss, diverse psychological, sociological and logistical factors can make it difficult for some individuals with T2DM to initiate, or adhere to, these lifestyle interventions (1, 9). With the number of people with T2DM continuing to rise, this pandemic is expected to reach 700 million people by 2045 (24). Thus, there is a clear need for cost-effective interventions that can effectively improve glycaemic control in people with T2DM and which people will adhere to.

A simple exposure to a lowered concentration of inspired oxygen (i.e. hypoxia) may represent such an intervention. In addition to the beneficial effects on glucose homeostasis that have been reported following a single acute hypoxic exposure, repeated intermittent, or continuous, hypoxic exposure may also have therapeutic potential in individuals with T2DM. In rodent models, daily hypoxic exposures returned fasting blood [glucose] to normal levels and increased glucose transporter 4 translocation in mice with T2DM (6, 35). Similar effects on glucose homeostasis have been shown in overweight humans (17) and those with insulin resistance, (during intermittent hypoxic training) which was explained, at least in part, by reduction in body mass (~ 1.2 kg) (27).

Another mechanism for hypoxia induced weight loss could be a shift in the gut microbiome. The gut is a hypoxic environment and as the body becomes systemically hypoxic, anaerobes are likely to become more dominant (11). Some anaerobes are fermenters which not only produce alcohol but also short and medium chain fatty acids which can be metabolised (2, 25). Specifically, the hypoxia-inducible factor (HIF) pathway is attenuated with upregulation of the pyruvate kinase 1 and subsequent inhibition of pyruvate dehydrogenase (21). Moreover, the gene encoding PPAR is selected for during high altitude which leads to a shift in fatty acid

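### The DEXA variables are named as tissue densities, which do not match the stated purpose of attributing weight loss to fat or fat-free mass

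*Combined protocol and SAP*

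**What the plan says.** The DEXA paragraph of section 10.4 plans a whole-body scan followed by a segmental analysis. It then states: "Variables that will be calculated from the scan data are fat density, muscle density and bone density". The same sentence adds that "the scan will produce a density value measured in" g·cm⁻³. The sentence after that gives the purpose: a baseline description of body composition, and a measurement that "will allow us to identify if the expected weight loss of the intervention is fat or fat free mass".

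The outcome served by the scan is listed under secondary outcome measures in section 7.2, in the run "body mass / composition change, hormonal markers of appetite (e.g. leptin and ghrelin), food intake, gut microbiome". The synopsis and section 6.2 name it in the same general way. None of the three gives a unit or a compartment.

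On timing, section 10 says of visits 2 to 5: "An OGTT, body composition and venous blood samples and a stool collection will occur on each visit". Scans are therefore taken before and after each condition.

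Section 14.2 lists the variables to be compared, among them "insulin sensitivity, eHSP70, IL-6, leptin, ghrelin, TNFa, SOD, HIF-1"α, but it names neither body mass nor any DEXA variable. Section 14.4 says that no SAP is needed beyond section 14.

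**The concern.** The purpose requires amounts: how many kilograms of fat, and how many of everything else, were lost. The variables listed are intensive quantities, mass divided by volume. A person can lose fat, or muscle, without the density of the remaining tissue changing. Anyone who derived exactly the variables listed would hold figures that do not address the question in the following sentence.

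At stake is the interpretation of one secondary outcome. Fat loss and lean loss of the same size mean different things for a treatment that may act partly through body weight, and the protocol says it wants to tell them apart. There is also a smaller issue of pre-specification. If the densities are set aside once the data are in, the choice between mass and percentage, and between whole-body and segmental values, will be made after the results can be seen. Section 15 justifies the radiation by the scan's accuracy in measuring bodily change, so the variables reported should deliver that.

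**Working it through.** The protocol gives no figure that depends on the DEXA variables, so there is nothing to reproduce. The check is of definitions and units, followed by a short illustration.

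**1. Dimensions.** For tissue *i*, density ρᵢ = mᵢ / Vᵢ. Recovering the mass needs mᵢ = ρᵢ × Vᵢ, and so needs the tissue volume. Section 10.4 gives ρ for fat, muscle and bone, but no V and no rule for turning densities into masses.

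**2. Search for a definition elsewhere.**

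- Synopsis, 6.2 and 7.2: the outcome is named in general terms only.
- Flow-chart key in section 10: DEXA is labelled as body composition, with no variable.
- Section 14.2: no body mass and no scan variable.

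No section names fat mass, lean or fat-free mass, or percentage fat as a variable to be derived. Section 10.4 is the only operational definition.

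**3. Illustration.** Inputs:

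- Weight loss of 1.2 kg: the approximate figure in section 4 for people with insulin resistance during intermittent hypoxic training. It is used only for scale.
- Starting fat 35 kg and lean 62 kg: assumed.
- Tissue densities 0.90 (fat) and 1.06 (lean) g·cm⁻³, the same as kg per litre: assumed, and held constant as tissue is lost.

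Volume after loss is V = m / ρ, and density is m / V. For the all-fat case:

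- fat mass = 35 − 1.2 = 33.8 kg
- fat volume = 33.8 / 0.90 = 37.56 L
- fat density = 33.8 / 37.56 = 0.90

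| 1.2 kg lost as | Fat density | Lean density | Fat mass (kg) | Lean mass (kg) |
|---|---|---|---|---|
| all fat | 0.90 | 1.06 | 35 − 1.2 = 33.8 | 62.0 |
| all lean | 0.90 | 1.06 | 35.0 | 62 − 1.2 = 60.8 |
| half each | 0.90 | 1.06 | 35 − 0.6 = 34.4 | 62 − 0.6 = 61.4 |

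The density columns are identical in all three rows, and the mass columns separate them. The unchanged densities follow directly from the constant-density assumption, so the table shows the logic and is not independent evidence. Other starting masses or densities give the same pattern as long as that assumption holds.

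**The case against.** The strongest reply is that this is loose wording in a description of the device. The paragraph states the real target, whole-body and segmental scans are planned at each of visits 2 to 5, and the outcome lists speak of composition, not density. This largely stands: the intention is clear, the error is probably one of wording, and no data collection is lost. It does not remove the point, because the density sentence is the only statement of what will be derived, and it gives a matching volumetric unit.

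A second reply is that an areal density, mass per scanned area, may have been meant. Such a value could move as tissue is lost, and the illustration would then not apply. The documents do not say so; the point holds for the unit as printed, and an areal reading would itself require a correction. Likewise, a single whole-body density can be converted to a fat fraction with a two-compartment model, but the protocol lists separate tissue densities and specifies no such model.

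Two stronger readings are tempting. A reader might infer that the hypothesis of reduced body mass (the fourth in section 6) cannot be tested. It can: total body mass answers it, and no listed hypothesis predicts which tissue is lost. A reader might also infer that the plan commits to an uninformative analysis of densities. Section 14.2 specifies no DEXA analysis of any kind, so the documents support only a mismatch of definition together with an omission from that list.

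**Conclusion.** The point holds in a limited form. As written, in g·cm⁻³, the three DEXA variables do not measure how much of each tissue is present and so do not fit the purpose stated in the next sentence. No other section supplies a volume, a conversion or an alternative variable.

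The consequence is confined to one secondary outcome, change in body composition. The primary endpoint and the sample size both rest on OGTT glucose and are untouched. No numerical effect on any stated figure can be given. The conclusion rests on reading density as mass per volume, as printed, and on tissue density staying roughly constant when tissue is lost. It is a minor correction, worth making because it is specific and almost free.

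**What to change.** - **Section 10.4, DEXA paragraph:** replace the density variables with fat mass and lean or fat-free mass in kg, whole body and segmental. Percentage fat and bone mineral content can be added if wanted. All come from the scans already planned at visits 2 to 5.
- **Section 14.2:** add these variables and total body mass to the analysis list, compared between hypoxia and sham.

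The cost is one rewritten sentence and one extended list. No additional scan, visit or radiation is involved, and the sample size does not change.
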